5.0 Enrollment/Randomization

The study will be posted on Clinicaltrials.gov in concordance with guidelines. 20 patients will be recruited by advertisement with a goal of 10 patients completing the study. Patients will be recruited within Vanderbilt University Medical Center and affiliated Neurologists, as well as local neurologists in Alabama, Kentucky, Tennessee and Georgia. Letters will also be sent to academic medical centers close by such as University of Kentucky, University of Tennessee, Emory University, and University of

Protocol Version #8:

Protocol Date:

10/04/2022

Alabama. Advertisements will list the contact information of the PI, as well as ,the research study nurse.

All patients will be contacted by the study nurse after response or in the Vanderbilt Neurology Neuromuscular Clinic. The patients will be given information about the study and a copy of the informed consent to look over. Patients interested in the study will be scheduled for screening visits within the Vanderbilt Clinical Research Center (CRC). At the time of their screening visit they will be consented according to the principles of the Declaration of Helsinki and 2018 Common Rule Requirements.

Within 3 weeks, if a patient is found to be eligible at the time of screening an enrollment visit will be scheduled. All patients will be prospectively entered into the study. No randomization or blinding will take place as this is an observational prospective study utilizing new procedures for a biomarker without change in therapy. All efforts will be made to recruit patients prior to therapy initiation without significantly delaying therapy.

Address for contact information will be Department of Neurology, [name], [name]. Phone number is [contact].

List the process for randomization and/or registration; list the address, phone number or website where the registration will take place.

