Treatment naïve patients will be initiated on IVIg treatment after baseline visit procedures are completed. This can occur later that day or within the next 14 days. Patients who are treatment naïve will be given a loading dose of 2 g/kg IV over 3-5 days at standard infusion rates which will take 4-6 hours daily, depending on comorbidities and age. Patients will receive acetaminophen and diphenhydramine as standard pre-infusion prophylactic treatment. Patients will receive Privigen which is FDA approved for CIDP treatment either at Vanderbilt University Medical Center hospital infusion center or outpatient infusion center depending on insurance. Patients will then have 1 g/kg IVIg infusions scheduled every 3 weeks for 6 months. Every attempt will be made to ensure Privigen will be used for IVIg product as it is FDA approved for CIDP, is temperature stable, and has no sucrose (26). No placebo will be used given this would be unethical. Patients will serve as their own controls, and the hypothesis is that percentage of segmental demyelination found should decrease as INCAT score and strength increases.

For patients previously treated:

Baseline visit will be arranged closest to the day prior to infusion to ensure the best possible baseline measurement. They will resume according to the patient's previous schedule. Patients will have up to 1.2 g/kg monthly to account for different patient management schedules and variation and patients will be on Privigen ideally.

Patients with escalating weakness not responding to IVIg will be allowed to try additional treatments but will be released from study. Additional treatment with prednisone up to 20 mg/day will be allowed but must be stable dosing and not escalating to avoid additional variability.

Patients will receive IVIg infusions q3 weeks. A monthly phone call will occur so the coordinator can confirm that patients are doing well, having no new treatment related side effects, and are receiving IVIg infusions either at home or in infusion centers.

Day 90, Visit 3:

Procedures (previously described):

History & Physical Exam: Note interval history.

MRC Score

INCAT Score

Skin Biopsy

Labs: BMP to check renal function

Day 180, Visit 4:

Procedures (previously described):

History & Physical Exam: Note interval history.

MRC Score

INCAT Score

Skin Biopsy

Labs: BMP to check renal function

Nerve conduction studies will be repeated from Baseline visit 1

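### Aim 2 pools patients who start IVIg after the baseline biopsy with patients already on it, so its change from baseline is a before-and-after treatment effect only in the first group

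*Protocol*

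**What the plan says.** Section 4.0 admits treatment-naive patients and patients within 6 months of starting treatment. Section 6.0 then handles them differently.

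- **Naive patients.** "Treatment naïve patients will be initiated on IVIg treatment after baseline visit procedures are completed". The start may be the same day or up to 14 days later. The protocol sets a 2 g/kg load, after which "Patients will then have 1 g/kg IVIg infusions scheduled every 3 weeks for 6 months".
- **Previously treated patients.** The baseline visit is placed on the day before the next infusion, as an approximate treatment nadir. Afterwards "They will resume according to the patient's previous schedule", and "Patients will have up to 1.2 g/kg monthly to account for different patient management schedules and variation".

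For both groups, "Patients will serve as their own controls". Section 6.0 also states, without naming a group: "Patients will receive IVIg infusions q3 weeks".

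Section 5.0 describes the study in one sentence: "No randomization or blinding will take place as this is an observational prospective study utilizing new procedures for a biomarker without change in therapy". The recruitment preference comes immediately after it: "All efforts will be made to recruit patients prior to therapy initiation without significantly delaying therapy". No minimum number of naive patients is set.

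For Aim 2, Section 10.0 specifies signed-rank tests of the primary biopsy outcomes at 3 and at 6 months against baseline, as tests of improvement after treatment. It draws no distinction by prior treatment. The same section says that no formal power calculation was made and that the data will allow future ones.

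**The concern.** A patient can act as his or her own control for the effect of IVIg only if the control measurement is taken without IVIg. That holds for naive patients. In a patient already on IVIg, the baseline biopsy may reflect several months of treatment, and any early recovery of myelin may already have happened. The later biopsies then show whether further change occurs while treatment continues, which is a different quantity.

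One pooled test averages the two quantities in a proportion settled by who happens to enrol. A null result could mean that IVIg does not affect dermal myelin, or that few completers were naive. A positive result would be hard to scale for the same reason. Because the pilot's main product is input for later studies, the change it reports should have one meaning.

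**Working it through.** **1. The two contrasts side by side (Sections 4.0, 6.0 and 10.0)**

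| | IVIg-naive | Previously IVIg-treated |
|---|---|---|
| Baseline biopsy | before any IVIg | on IVIg, day before an infusion |
| IVIg after baseline | load, then protocol-set maintenance | own schedule resumed |
| Baseline to Day 90 or 180 | before versus after IVIg | change on continued treatment |
| Aim 2 test | pooled signed-rank | pooled signed-rank |

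Time on IVIg also differs. Naive patients may start up to 14 days after baseline, so their Day 90 biopsy follows 76 to 90 days of treatment (90 − 14 = 76). Previously treated patients bring up to about 6 months more. That is not a firm limit, because duration is checked at screening and baseline can be up to 30 days later.

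**2. Dilution of the mean change**

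The protocol gives no power or expected effect to reproduce. From Section 6.0 come a meaningful change of more than 5 points and an SD of 4.1 points in the previous study; from Sections 5.0 and 10.0, 10 completers. Assumed: naive patients change by 5 points, the others by 0 to 2.5, and the naive share is 8 or 5 of 10.

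Pooled mean = (n naive × 5 + n treated × d) / 10

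- 8 naive: (8×5 + 2×0)/10 = 4.0, to (8×5 + 2×2.5)/10 = 4.5
- 5 naive: (5×5 + 5×0)/10 = 2.5, to (5×5 + 5×2.5)/10 = 3.75

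**3. Illustrative power**

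The test is the exact two-sided signed-rank test with n = 10, rejecting when the smaller rank sum is at most 8 (actual alpha 0.049). Changes are simulated as normal. The SD of change is unknown, so three values are tried:

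- 4.1: the earlier study's SD taken directly as the SD of change.
- 5.8: 4.1 × √2, for uncorrelated visits.
- 10.7: counting error alone with 25 independent fibres and rates of 20% and 15%. The standard errors are √(0.20×0.80/25) = 8.0 points and √(0.15×0.85/25) = 7.1 points, and √(8.0² + 7.1²) = 10.7.

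| SD of change | 10 naive | 5 naive, others change 0 to 2.5 |
|---|---|---|
| 4.1 | 0.92 | 0.26 to 0.68 |
| 5.8 | 0.66 | 0.17 to 0.41 |
| 10.7 | 0.25 | 0.09 to 0.16 |

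Pooling lowers power at every SD tried. At 10.7 the test is weak even with all patients naive.

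**4. Illustrative size of a later paired study**

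For 80% power at two-sided 0.05, with SD 10.7 plus the variance added by mixing the groups, 39 patients are needed if sized on the naive change. Sized on the pooled change, the number is 47 to 61 with 8 of 10 naive and 68 to 155 with 5 of 10 naive.

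**5. What separate reporting can deliver**

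With 5 naive completers the 95% half-width is 2.776 × SD/√5. That is 5.1 points at an SD of 4.1 and 13.3 at 10.7. The smallest two-sided signed-rank p-value with 5 patients is 2/2⁵ = 0.0625, so a test in that group could not reach 0.05; with 6 patients it is 2/2⁶ = 0.031.

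**The case against.** The best case for the plan is that the mixing is deliberate and limited. Entry is confined to early treatment, the on-treatment baseline is placed at the infusion nadir, naive patients are preferred, and this is a hypothesis-generating pilot with no power claim. Medical history and concomitant medications are recorded, so the naive change could be extracted later, and a statistical analysis plan may already provide for it. All of this lowers the stakes. It does not remove the point: a nadir is still on treatment, the recruitment preference sets no minimum, and Section 10.0 itself fixes one comparison with one interpretation.

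Four stronger readings are tempting, and the document does not support them.

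- *The Section 5.0 sentence is a design contradiction.* A reader might infer from it that no patient's therapy changes. The next sentence refers to recruiting before therapy begins, and Section 6.0 sets out both regimens. The phrase is loose and can mean no departure from usual care.
- *The doses conflict.* One might set 1 g/kg every 21 days (30/21 = 1.43 g/kg per 30 days) against the 1.2 g/kg monthly ceiling. The 1 g/kg dose belongs to naive patients, and the general 3-weekly sentence states no dose. A dose of 0.8 g/kg every 21 days is 1.14 g/kg per 30 days, within the ceiling. Only the interval conflicts with resuming the previous schedule.
- *Aim 2 loses a known amount of power.* The naive share, the treated-group change and the SD of change are all assumed. The power with 10 naive patients alone ranges from 0.25 to 0.92.
- *A later trial will be sized wrongly.* Section 10.0 does not say that the pooled change will be the planning input.

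**Conclusion.** The point holds as one of interpretation. The Aim 2 change from baseline is before versus after IVIg only in IVIg-naive patients; in patients already on IVIg at baseline it is change on continued treatment. The protocol tests the two together as one treatment improvement.

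That conclusion rests on the text alone. The direction of the effect needs one assumption, that previously treated patients change less than naive ones; if they change equally, the pooled mean is not diluted. The size cannot be determined from the protocol. Halving a 5-point change to 2.5 requires half the completers to be previously treated and stable. All power and future sample-size figures are illustrations.

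The change is worth making because it costs little and gives the pilot's main estimate one meaning. The study is not invalid without it.

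**What to change.** **Section 10.0, Aim 2**

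- Keep the pooled signed-rank tests.
- Also report the Day 90 and Day 180 change, with an interval, separately for IVIg-naive and previously IVIg-treated patients. Define the split by IVIg exposure, since the screening limit refers to any CIDP treatment and prednisone is allowed.
- Use the naive change as the before-and-after estimate for interpretation and for sizing later studies. Label the other *change on continued treatment*.
- Derive months since first IVIg at each biopsy.

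**Minor wording**

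- Section 5.0: state that naive patients start IVIg as set out in Section 6.0 and that previously treated patients continue their own regimen.
- Section 6.0: limit the general 3-weekly infusion sentence to naive patients, because its interval conflicts with resuming a previous schedule.

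**Cost.** A few sentences and one derived variable, taken from treatment history, concomitant medications and the monthly calls already planned. No patients, visits or biopsies are added and no test is lost. The drawback is precision: with 5 naive completers the interval is about ±5 points at an SD of change of 4.1 and ±13 at 10.7, both assumed SDs. The split should therefore be reported as estimates with intervals and not as subgroup tests.

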6.0 Study Procedures

Day -30 -0, Visit 1: Screening visit:

Procedures:

Consent: Patients will provide written consent according to the principles of the 2018 Common Rule and Declaration of Helsinki

H&P: Detailed history and physical with neurological examination will be performed.

MRC score: Medical Research Council (MRC) score for muscle strength will be performed.

Nerve Conduction Studies: Limbs will be warmed to at least 31 C minimum temperature. Antidromic sensory nerve conduction studies of the sural, median and ulnar nerve will be performed. Motor conduction studies of the peroneal, tibial, ulnar and median with proximal studies and F-waves will be performed. Unless patients have significant asymmetry, all studies will be done on the left. Conduction block and temporal dispersion will be noted.

Labs: Blood will be drawn for CBCPD, IgA, CMP. If previously performed will record CSF protein and cell count.

If patients are found to have history and exam consistent with CIDP, met ENFS criteria (cite), inclusion, exclusion criteria including less than 6 months of treatment for CIDP

Protocol Version #8:

Protocol Date:

10/04/2022

they will be accepted into the study and baseline visit will be scheduled 24 hours to 30 days apart. No randomization will take place as all patients will be treated.

Day 1, Visit 2: Baseline visit:

Patients qualifying for the study will be invited back for baseline visit. If patients have not been on IVIg treatment this visit will be scheduled as soon as possible to avoid delays in treatment. If patients have been started on IVIg treatment, patients will be scheduled the day before their next infusion to approximate a nadir in treatment for best baseline measurement.

Procedures:

Physical exam: Interval history will be taken (if appropriate) and physical exam with neurological examination repeated.

MRC score: MRC score will be documented.

INCAT score: The INCAT score will be collected as a secondary endpoint as it has been used in both ICE and PATH studies (refs). The INCAT score for upper and lower extremities will be documented.

Skin biopsies:

Skin biopsies will be performed at the second study visit. The procedure below is similar to that of Li et al. 2005 (16). The biopsy is performed on the lateral aspect of the finger between the first and second interphalangeal joint 2-3 mm from the border of the hairy skin of the finger. The area is anesthetized with 1% lidocaine with epinephrine. A 2 mm punch is used with tip length of 8 mm (Miltex Instrument Co.). The skin punch is pushed perpendicularly to the surface of the skin and advanced to a depth of 5 mm (a little over half way to the punch tip). The biopsy wound will be compressed for at least 15 minutes as the fingers are rich in small vessels to stop bleeding. A bandage will be applied over the wound. Patients will be instructed to change the bandage daily until the wound is healed and to avoid immersing their fingers in water for prolonged periods until a scab has formed. The digit nerves and arteries are deeper than 5 mm and should not be harmed by the procedure.

Biopsies are preserved by 4% paraformaldehyde fixative for 30 minutes, followed by cryoprotection in phosphate-buffered sucrose solution. Sectioning will be done in a -20°C temperature-regulated cryostat (Leica CM1950) after embedding in optimal cutting temperature (OCT) medium. Relatively thick sections of 60 µm will allow for capture and potentially reconstruction of large structures like internodes, Meissner corpuscles, etc. (8). This yields approximately 20-24 sections per biopsy.

Immunohistochemistry: Aim 1 will be achieved by immunostaining multiple neuronal structures conjugated with fluorophores of various wavelengths (e.g. Dy488, Cy3, Dy649; Jackson Immunoresearch) in order to identify the pan axonal marker, protein gene product 9.5 (PGP 9.5; AbD serotec), compact myelin basic protein (MBP; Chemicon) and voltage-gated sodium channels (Pan NaV; Sigma-Aldrich). Four sections of each biopsy will be stained with MBP, PGP 9.5 and PanNaV markers. Additional sections will be reserved for future exploratory measures.

Epifluorescence microscopy (Leica DM4000) will be sufficient for identifying and measuring Pan NaV-immunoreactive nodes of Ranvier, length of sections for density calculations, as well as other cutaneous structures. Internodal length will be measured three dimensionally (Metamorph) in confocal-acquired images (Leica LSM510). Quantitative morphometric parameters of dermal myelinated fibers include Meissner corpuscle density (receptors per mm²), the density of their myelinated afferents (fibers per mm², axon diameter (µm), and further characterization of myelin structure in regards to internodal, nodal and paranodal length (µm) will also be calculated. Based on morphologic analyses, additional measures unique to dermal myelinated fibers may be generated and ROC curves developed to determine sensitivity and specificity. Confocal microscopy will be utilized in 3 patients at each site to confirm nodal measurements, myelinated fiber density, and confirm presence of segmental demyelination. Correlation of confocal measurements with florescence measurements will be evaluated to determine whether florescence is sufficient for accurate measurements. The PI and [name] will be analyzing the samples in a blinded fashion, and will train lab technicians in this technique which [name] and [name] have published.

Analysis of segmental demyelination: Measurement of myelinated fiber density from glabrous skin biopsies will be calculated according to methods of previous publication (7, 23, 24). Meissner corpuscle density will also be performed for comparison. Number of papillary, dermal internodes will be calculated. Analysis of nodes of Ranvier will include quantitation of nodes with greater width (> 6 µm; (25)); branching at nodes, localization of ion channels within nodes will be quantified from 25 nodes from each biopsy, using at least 3 sections to ensure random distribution. Given the previous normal healthy control data demonstrating a 5% rate for healthy controls and 7.7% in diabetic subjects, 20% will be used as the cutoff for CIDP. 15.7% was the 95th percentile observed in both diabetic and healthy controls, with one diabetic subject having a 15% demyelination rate. Given that [name] observe demyelination in multiple fibers from previous CIDP patients sampled, we believe this will ensure diagnostic efficiency with sufficient sensitivity (9). It is unknown what treatment effects we will find, but given the standard deviation was 4.1% in the previous study, we would expect a change greater than 5% to be meaningful.

Further characterization of nodal and internodal integrity for aim 1 will be investigated with nodal staining using pan-sodium channels (7), the paranodal staining of Contactin-associated protein (Caspr; Neuromab) and internodes will be labeled by staining for myelin basic protein (MBP). These will be helpful to further measure nodal width and alsoand to evaluate for decompartmentalization of ion channels which channels, which could contribute to conduction block. An internode will be defined as a segment with intact MBP, Pan-Na and PGP9.5 staining demonstrating a node on each end. A total number of nodes per biopsy (in 4 sections) will be calculated. We will estimate segmental demyelination percentage by calculating numbers of fibers with demyelination (identified as gaps of MBP stain within a fiber where MBP stain is visible on both sides of gap and PGP 9.5 stain is present confirming axonal integrity)/total number of fibers counted (25). Repeated measures for each patient will be calculated to determine if there is decrease in segmental demyelination over time after treatment.

IVIg infusions:

Protocol Version #8:

9

Protocol Date:

10/04/2022

Treatment naïve patients will be initiated on IVIg treatment after baseline visit procedures are completed. This can occur later that day or within the next 14 days. Patients who are treatment naïve will be given a loading dose of 2 g/kg IV over 3-5 days at standard infusion rates which will take 4-6 hours daily, depending on comorbidities and age. Patients will receive acetaminophen and diphenhydramine as standard pre-infusion prophylactic treatment. Patients will receive Privigen which is FDA approved for CIDP treatment either at Vanderbilt University Medical Center hospital infusion center or outpatient infusion center depending on insurance. Patients will then have 1 g/kg IVIg infusions scheduled every 3 weeks for 6 months. Every attempt will be made to ensure Privigen will be used for IVIg product as it is FDA approved for CIDP, is temperature stable, and has no sucrose (26). No placebo will be used given this would be unethical. Patients will serve as their own controls, and the hypothesis is that percentage of segmental demyelination found should decrease as INCAT score and strength increases.

For patients previously treated:

Baseline visit will be arranged closest to the day prior to infusion to ensure the best possible baseline measurement. They will resume according to the patient's previous schedule. Patients will have up to 1.2 g/kg monthly to account for different patient management schedules and variation and patients will be on Privigen ideally.

Patients with escalating weakness not responding to IVIg will be allowed to try additional treatments but will be released from study. Additional treatment with prednisone up to 20 mg/day will be allowed but must be stable dosing and not escalating to avoid additional variability.

Patients will receive IVIg infusions q3 weeks. A monthly phone call will occur so the coordinator can confirm that patients are doing well, having no new treatment related side effects, and are receiving IVIg infusions either at home or in infusion centers.

Day 90, Visit 3:

Procedures (previously described):

History & Physical Exam: Note interval history.

MRC Score

INCAT Score

Skin Biopsy

Labs: BMP to check renal function

Day 180, Visit 4:

Procedures (previously described):

History & Physical Exam: Note interval history.

MRC Score

INCAT Score

Skin Biopsy

Labs: BMP to check renal function

Nerve conduction studies will be repeated from Baseline visit 1

Data Entry Study data will be collected on paper forms for each study procedure and entered into Redcap database. All Data entry will be reviewed by PI and team for accuracy. Use of Redcap will also provide tracking of data entry and security. Protocol compliance will be monitored by PI and investigator team.

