2.0 Rationale and Specific Aims

Study Hypothesis and Objectives:

Chronic inflammatory demyelinating polyneuropathy (CIDP) is a chronic, disabling illness where there is immune-modulated demyelination of motor and sensory myelinated axons. Unlike most polyneuropathies, CIDP is treatable, and responds to multiple immunotherapies, the most effective being intravenous immunoglobulin (12). Newer approaches include subcutaneous immunoglobulin (SCIg) which has been used successfully for other patients and has shown promise in the treatment of CIDP (13).

The main treatment of CIDP has been intravenous immunoglobulin (IVIg), typically given in pulses or repeated treatments every 3 to 6 weeks. About 50-70% of patients respond to IVIg treatment (14) as opposed to 40% of patients on prednisolone or 30-88% of patient to plasma exchange, but is difficult to deliver repeatedly (15-17). The goal of immunoglobulins or immunosuppressive therapy is to prevent demyelination which is secondary to autoimmune –mediated damage to peripheral sensory and motor nerves.

The major barrier to treating patients effectively has been identifying correctly patients with CIDP who will respond to immunomodulatory treatment. Nerve conduction studies and nerve biopsy are insensitive at identifying patients with acquired demyelination. Skin biopsy has been used as a diagnostic tool for neuropathies. Biopsy of glabrous skin can be repeated over time and using antibodies to myelin antigens tagged with florescent proteins, can demonstrate demyelination, and abnormalities at the node of Ranvier (gaps in myelin where

Protocol Version #8:

Protocol Date:

10/04/2022

salutatory conduction takes place, important for axon potential propagation in myelinated nerves), in addition to quantifying density of myelinated fibers present, (18, 19). Segmental demyelination has been shown to be present in glabrous skin biopsies of CIDP patients (10) in a previous small study.

We hypothesize that dermal myelinated fibers in glabrous skin biopsies show segmental demyelination in CIDP patients, which will improve over time with treatment.

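### For patients already on IVIg, the baseline biopsy is set at the pre-infusion nadir, but the Day 90 and Day 180 biopsies are not tied to the infusion cycle

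*Protocol*

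**What the plan says.** Section 4.0 of the Protocol admits both treatment-naive patients and patients within 6 months of starting treatment. For those already on IVIg, Section 6.0 sets the baseline visit, which includes the biopsy and the MRC and INCAT scores, by the infusion cycle: "patients will be scheduled the day before their next infusion to approximate a nadir in treatment for best baseline measurement". The IVIg part of the same section repeats the rule: "Baseline visit will be arranged closest to the day prior to infusion to ensure the best possible baseline measurement".

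The follow-up visits have no such rule. Section 6.0 labels the last one only "Day 180, Visit 4" and the one before it Day 90. Appendix A gives the same two days, without a window or a link to an infusion.

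On infusion timing, naive patients start after baseline ("This can occur later that day or within the next 14 days") and then follow a fixed interval: "Patients will then have 1 g/kg IVIg infusions scheduled every 3 weeks for 6 months". For previously treated patients the text reads "They will resume according to the patient's previous schedule", yet a general statement in the same part reads "Patients will receive IVIg infusions q3 weeks". Section 2.0 describes IVIg as "typically given in pulses or repeated treatments every 3 to 6 weeks".

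Section 10.0 compares the primary outcomes at 3 and at 6 months with baseline by signed rank tests for improvement after treatment. It does not distinguish the two kinds of patient.

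**The concern.** Aim 2 is a within-patient comparison, with each patient as their own control. For previously treated patients the protocol controls cycle phase at the first measurement and leaves it free at the other two. If the outcomes vary over the infusion cycle, a baseline at trough and a follow-up some days after an infusion differ by phase as well as by time, and the phase part points the same way as the hypothesised improvement. If they do not vary, the baseline rule has no purpose. A biopsy cannot be re-timed afterwards, so no analysis plan can repair this.

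There is a second, smaller point. A naive patient's change is a before/after change. A previously treated patient's change occurs during continuing therapy, with Visits 3 and 4 up to about 6 + 3 = 9 and 6 + 6 = 12 months after treatment onset. Calling both improvement after treatment mixes two quantities.

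**Working it through.** The plan states no figure to reproduce here. The check is cycle arithmetic.

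**Does the nadir rule carry forward?** At Visits 3 and 4 the remark that items were described before is attached to the procedures, not to scheduling. No other text ties these visits to an infusion.

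**Previously treated patients.** Inputs: baseline on Day 1 (Section 6.0), infusion the next day (Day 2), visits exactly on Days 90 and 180, no slippage. Cycle lengths c cover the 3 to 6 weeks in Section 2.0.

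- Days since last infusion = (visit day − 2) mod c. For c = 21: 88 mod 21 = 4 and 178 mod 21 = 10.
- Days since last infusion at baseline, with the earlier infusion on schedule = c − 1.
- Pre-infusion days are 1 + ck for whole k. The shift is the distance from Day 90 or Day 180 to the nearest of these.

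| Cycle (days) | At baseline | At Day 90 | At Day 180 | Nearest pre-infusion days | Shift (days) |
|---|---|---|---|---|---|
| 21 | 20 | 4 | 10 | 85, 190 | 5, 10 |
| 28 | 27 | 4 | 10 | 85, 169 | 5, 11 |
| 30 | 29 | 28 | 28 | 91, 181 | 1, 1 |
| 35 | 34 | 18 | 3 | 106, 176 | 16, 4 |
| 42 | 41 | 4 | 10 | 85, 169 | 5, 11 |

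Only the 30-day cycle keeps follow-up near the baseline phase.

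**Naive patients.** Their baseline precedes any IVIg, so it has no phase to mismatch. With the first loading day s on Day 1 to 15 and infusions every 21 days counted from s, (90 − s) mod 21 is 0–5 or 12–20 days and (180 − s) mod 21 is 0–11 or 18–20 days. Follow-up phase therefore varies between patients. On a 21-day cycle the nearest pre-infusion day is at most 10 days away.

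**What a phase effect could do (illustration only).** Assume all 10 completers were previously treated, with no true trough-to-trough change, normal changes and a two-sided exact signed rank test at 0.05 (4,000 simulated runs per setting). Take the SD of change as 4.1 points (the SD in Section 6.0 used directly) or 4.1 × √2 = 5.8. A phase difference of 1 point gives a significant result in about 10% or 8% of runs, and one of 2.5 points in about 39% or 22%. With no phase difference it is about 5% for both SDs. The phase differences are assumed, and an all-treated sample is the extreme case.

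**Baseline day.** Section 6.0 puts Visit 2 on Day 1; Appendix A puts it on Day 1 to 30. A Day 1 baseline gives 90 − 1 = 89 and 180 − 1 = 179 days to Visits 3 and 4. A Day 30 baseline, with the later days counted from a fixed Day 1, gives 60 and 150.

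**The case against.** The harm is conditional. Nothing in the documents shows that segmental demyelination varies within an infusion cycle. The nadir sentence schedules a whole visit, including the clinical scores, and makes no claim about the biopsy. That stands: the size, and even the presence, of a bias is unknown.

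The 4- and 10-day figures need exact dates and a given cycle, and a 30-day cycle nearly removes the mismatch. Section 4.0 expresses the dose range per 30 days, so a monthly schedule is plausible for some patients. That also stands, but the protocol neither requires that cycle nor makes the follow-up phase match on the others.

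Section 5.0 aims to recruit before therapy starts, so previously treated patients may be few. No limit is set, however. Infusion dates might be recovered from concomitant-medication records or the monthly calls, but no text requires days since infusion to be recorded at a biopsy.

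Separate results for naive and treated patients could sit in an analysis plan that is not shown. This is why that part is secondary. Biopsy timing is a protocol matter.

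A reader might infer more than the text supports:

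- That Aim 2 rests on one test. Section 10.0 names three primary outcomes at two time points, 3 × 2 = 6 comparisons. What they share is the pooling of patients.
- That the pooled change would mis-size a later trial by some factor. Any such factor would rest on assumed effects and an assumed mix of patients, so none is claimed.
- That naive patients' changes are biased in the same way. They have no baseline phase; uncontrolled follow-up phase could at most add scatter, and only if phase matters.

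**Conclusion.** The inconsistency is real: phase is controlled at baseline and uncontrolled at both follow-up biopsies. On a 3-week cycle, previously treated patients are compared at 20 days after an infusion (baseline) and then at 4 and 10 days, assuming infusion on Day 2 and no slippage. The mismatch is present on the 21-, 28-, 35- and 42-day cycles and nearly absent on 30 days. Whether it produces apparent improvement depends on a phase effect that the documents do not give and on a number of patients that they do not fix. The mixing of before/after and on-treatment change is a secondary problem of interpretation.

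Severity is minor to should-fix. The study is a hypothesis-generating pilot without a power calculation, but its data are meant to support later power calculations, and the timing can be settled only before the biopsies are taken.

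**What to change.** - **Section 6.0 and Appendix A:** for patients then on IVIg, hold Visits 3 and 4 on the pre-infusion day nearest Day 90 and Day 180, leaving infusion dates unchanged. If no infusion is scheduled after Visit 4, use the same number of days since the last one.
- **At every biopsy:** record days since last infusion and time since first IVIg.
- **Section 10.0:** show Aim 2 changes separately for naive and previously treated patients as descriptive results, and describe only the naive change as a before/after response.
- **Reconcile:** the two statements on infusion interval for previously treated patients (own earlier schedule, or every 3 weeks), and the two definitions of the baseline day (Day 1, or Day 1 to 30). Which is right is for the investigators to say.

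The cost is some wording and two recorded items; the monthly calls already check infusions. Visits move by 5 and 10 days on a 3-week cycle and by at most 16 days on the cycles examined, so the time from baseline becomes less uniform. The separate results will be small: with five or fewer patients in a group, the two-sided signed rank p-value cannot fall below 2/2⁵ = 0.0625, so they should stay descriptive.
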